# 11.3 Donor HLA Antibody

We will assess for the development of donor-specific antibodies as they have been implicated as a risk factor for acute rejection, chronic rejection, and the development of fibrosis (Musat, 2011) (Paterno, 2012) (Kaneku, 2012).

Serum samples collected from participants at time points after liver transplantation as specified in the SOE and will be evaluated for the presence or absence of donor-specific alloantibodies. Assessments will include donor-specific crossmatching with cryopreserved cells, testing against a panel of cryopreserved lymphocytes and/or HLA antigen-coated microparticles.

# 11.4 Histology and Multiplex Immunohistochemistry

In collaboration with Dr. [name], we will perform extensive histology and mIHC analysis of protocol biopsy samples obtained prior to darTreg infusion and 1 week after darTreg infusion. The cohort that does not receive darTreg will get a single biopsy at 12 weeks after transplantation, the approximate time of darTreg infusion for the other groups. The design of these analyses will be guided by histology and mIHC data from tolerant patients in the [name] Immunosuppression Withdrawal trial and our current understanding of liver transplant tolerance. Histological analyses will evaluate 40 histopathological features to determine tissue integrity and degree of inflammation. mIHC analyses are summarized in *Table 4. mIHC Markers*.

Table 5. mIHC Markers

mIHC Panel	Rationale
C4d/CD31	Decrease in C4d deposits on the hepatic microvasculature is associated with liver transplant tolerance.
C40/CD31	Determine if Treg therapy leads to decrease in C4d deposits
CD3/γδ -1/ γδ -2	Portal tract ratio of $y\delta$ -1/ $y\delta$ -2 >1.0 is associated with operational tolerance. Determine if Treg therapy
CD3/y0 -1/ y0 -2	promotes this signature
CD3/CD45RO/CD45RA	Monitor the relative ratio of naïve to memory T cells; test the hypothesis that Treg therapy leads to a
CD3/CD43RO/CD43RA	reduction in portal-based CD3+/CD45RO+ (memory) T cells
CD4/Tbet/GATA-3/IL-	Monitor the polarization of CD4+ lymphocytes within the allograft to determine whether an increase of
17/FoxP3	putative Tregs contributes to tolerance.
IL10/TGFβ/HLADR	Monitor expression of immunomodulatory cytokines by HLA-DR expressing cells in the liver such as Kupffer
ILIO/ IGPP/ ILADK	and B cells.
CK19/CD31/HLADR	Up-regulation of HLA-DR on biliary epithelium (CK19+) and vascular endothelium (CD31+) makes these cells
CK13/CD31/HLADK	targets of immune rejection. Determine if Treg therapy prevents DR induction.

#### 11.5 Deuterium Labeling and Detection

Our clinical trial relies on transferring darTregs that have been expanded hundreds-of-fold *in vitro*. These cells will be indistinguishable from endogenous Tregs by standard surface markers; therefore we will not be able to distinguish administered darTregs from endogenous Tregs. Because the cells are being expanded prior to infusion, it provides a unique opportunity to label the cells prior to infusion to monitor engraftment and persistence of the administered darTregs. For over a decade, the [name] group, and others, using their techniques have applied stable isotope labeling with mass spectrometric analysis to measure the replication of murine and human cells *in vitro* and *in vivo*. Importantly, stable isotopes are non-radioactive and non-toxic (Klein PD, 1986) (Koletzko B1, 1997), and they have been safely used as cellular, molecular, and metabolic markers in patients and healthy controls for more than 6 decades (Klein PD, 1986) (Koletzko B1, 1997).

Confidential Page 53 of 80

In Protocol RTB-002, Tregs from transplant patients will be labeled with deuterium by including the H label in the culture medium during the entirety of the expansion phase in vitro (day 0 to day 14) prior to infusion in the patient. Based on data from in vitro labeling studies, we expect the cells to be ~60% enriched for H. After infusion, PBMCs will be isolated and stored at specified time points as described in the SOE. DNA prepared from these samples will be analyzed by gas chromatography-mass spectrometry. Based on prior studies, we expect sensitivities in the range of approximately ±0.05 to 0.10% enrichment (which refers to the fraction of labeled molecules) (Busch, 2007) (Macallan, 1998). As detailed in Section 1.2.2, we expect the patients to have about 5 x 109 endogenous Tregs 10 to 13 weeks after Thymoglobulin® treatment. Therefore, an infusion of 200 and 800 x 10^6 darTreg in the higher dose groups will likely result in a detectable increase in overall Treg numbers, detectable by TruCount (BD Biosciences) and MFC assays (Section 10.2) at early time points. Deuterium labeling will allow investigators to distinguish between infused darTregs and endogenous Tregs, thus unequivocally demonstrate the presence of infused darTregs in the periphery. Similarly, presence of deuterium-labeled Tregs in the graft will be determined by analyzing genomic DNA extracted from FACS-purified CD4+ cells isolated from biopsy tissues collected at 1 week after darTreg infusion and at the time of rejection. Deuterium labeling will be detectable for at least 4 cell divisions of the administered darTregs. We expect this method of detection to be especially advantageous at early time points (up to 28 days) post infusion, prior to significant division, exit into tissues, and/or loss of darTregs.

### 11.6 TCR Sequencing

Recent advances in sequencing technologies have led to PCR based strategies to detect rare T cell clones based on a unique TCR sequence. Sensitivities of up to 1 in 100,000 cells have been reported (Robins, 2012) with this technique. Using this technology, we have analyzed TCR usage of expanded darTregs. Our results demonstrate that the repertoire of darTregs is narrower than the repertoire of Tregs freshly isolated from peripheral blood, but remained highly diverse. The highest frequency of a single T cell clone in the darTreg product was around 1% and the top 20 clones collectively represented 5 to 10% of the total population. Interestingly, by comparing the repertoire before and after expansion, we have found that the top 20 clones mostly undetectable in the pre-expansion Treg samples. This suggests that we will be able to identify darTregs after infusion using TCR analysis. We will determine the top clones in darTregs using sequencing and detect the top clones after infusion using PCR. Although this technology may allow us to track cells early after infusion, this technique has the potential to be complementary to the deuterium labeling approach. Deuterium labeling may be advantageous early after infusion as the percentage of labeled cells will be high. However, with cell division, signal will be difficult to detect after approximately 4 divisions. The deuterium labeling approach has already proved successful in the Type I diabetes trial with polyclonally expanded Treg. TCR sequencing may potentially be less sensitive early, depending on the degree of oligoclonality; however, if successful clones persist and divide over time in patients, these clones will give a stronger signal over time. PBMCs will be sorted for Treg from frozen, banked specimens and cell pellets will be used for TCR sequencing by Adaptive Biotechnologies.

Confidential Page 54 of 80

# 12. Biospecimen Storage

Whole blood or leukapheresis samples for Treg manufacturing will be collected and cryopreserved in aliquots according to established SOPs and stored in UCSF GMP cell manufacturing facility. Some of the aliquots will be sent to ITN repository for mechanistic studies.

Samples collected solely for mechanistic studies will be sent to the ITN repository and stored under specific conditions to maintain long-term sample integrity, as well as specimen tracking from receipt to shipment to alternate locations. A 21 CFR Part 11 validated database system can be used to track shipment date, location shipped to, carrier, items shipped, amount shipped, barcode numbers, protocol number, and associated comments about each individual specimen. Storage temperature, location, processing and aliquoting, and freeze/thaw events may also be recorded.

If the study subject allows storage, the subject's specimens will be stored indefinitely. The subject can change their mind at any time and have their stored specimens destroyed by notifying the study physician in writing. In such cases, the site coordinator would send all requests for sample destruction to the ITN. The site will receive confirmation that the specimen was destroyed as requested. If the subject's samples have already been analyzed, then the data will be used as part of the overall analysis. The subject can only request to have samples destroyed if they still exist, i.e. have not already been used in an experiment.

Specimens at the ITN core or repository can only be transferred to another destination with appropriate authorization per ITN standard procedures. Purpose for accessing/transferring the specimen (within study assay as defined by the protocol or future studies), evaluation of subject consent for the purpose provided, verification of specimen identifiers, and quality and quantity of the specimen are some of the items checked prior to authorization.

If the purpose is for future studies, and the subject consents for storage for future use, the subject's sample may be made available to the scientific research community per the ITN Sample Sharing Policy (www.immunetolerancenetwork.org). Any research conducted using stored samples for future use may also need appropriate regulatory approval, such as Institutional Review Board (IRB) per the study consent.

Exceptions to the above banking condition apply to the samples used for Treg TruCount, and deuterium detection in blood and biopsies because the assays need to be performed on fresh samples. Donor specimens will be stored until the end of study analyses and then be destroyed or anonymized.

Confidential Page 55 of 80

### 13. Criteria for Participant Completion and Premature Study Termination

# 13.1 Participant Completion

Subjects in Cohorts 1a and 1b who have completed assessments at all study visits outlined in the SOE after lymphocyte depletion with Thymoglobulin° and TAC- or EVR-based Treg supportive IS regimen will have completed the study. Subjects in Cohorts 2, 3, and 4 who have completed assessments at all study visits outlined in the schedule of events after receiving Thymoglobulin°, Treg supportive IS, and darTreg infusion will have completed the study. The site PI will determine whether these participants should continue with the Treg supportive IS regimen or whether these participants should be converted to the site's standard of care IS regimen.

#### 13.2 Participant Withdrawal Criteria

Participants may be prematurely terminated from the study without any further follow-up for the following reasons:

- 1. The participant elects to withdraw consent from all future study activities, including follow-up
- 2. The participant is "lost to follow-up" (i.e., no further follow-up is possible because attempts to reestablish contact with the participant have failed)
- 3. The participant dies
- 4. If a participant prematurely terminates from the study because of graft loss, because the investigator no longer believes participation is in the best interest of the participant or because of non-compliance with follow-up and/or study procedures, follow-up should be according to the safety follow-up schedules of events (*Section 13.4*).

### 13.3 Participant Replacement

Any participant who is deemed ineligible to initiate Thymoglobulin° (Stage 2, Screening B) will be replaced. Any participant in Cohorts 2, 3, or 4 in whom Thymoglobulin° has been administered but is then deemed ineligible to receive darTreg infusion (Stage 3, Screening D) will be replaced if deemed appropriate after review by the NIAID MM, PI, and two transplant physicians independent of this study. This does not replace or change the stopping rules detailed in *Section 14.8.1* . All decisions made related to participant replacement in this stage will be reviewed during the standard DSMB review as described in *Section 14.8.1* Any participant who has received any part of a darTreg infusion (Stage 3) and subsequently terminates from this study prematurely will not be replaced.

#### 13.4 Follow-up after Early Study Withdrawal

# 13.4.1 Follow-up after Premature Discontinuation from Stage 1

Subjects who are prematurely withdrawn from Stage 1 of the study will be terminated from the study and will not be followed. Subjects who move to Stage 2 but discontinue from the trial prior to receiving study directed Thymoglobulin will not be followed.

# 13.4.2 Follow-up after Premature Discontinuation from Stage 2 or Stage 3

All subjects who are prematurely withdrawn from Stage 2 and have received any study directed Thymoglobulin® (without receiving darTregs) will have a safety follow up visit 4 weeks after stopping study therapy (Appendix 4). In addition, these subjects will continue the safety follow up schedule (Appendix 4) until 40 weeks after transplantation. Subjects prematurely discontinuing study therapy from Stage 3 after receiving any part of a darTreg infusion will be followed according to Appendix 5 starting with a follow up visit within 4 weeks after the decision to stop study therapy.

Confidential Page 56 of 80

### 14. Safety Monitoring and Reporting

#### 14.1 Overview

This section defines the types of safety data that will be collected under this protocol and outlines the procedures for appropriately collecting, grading, recording, and reporting those data. AEs that are classified as serious according to the definition of health authorities must be reported promptly to the sponsor DAIT/NIAID or other Sponsor. Appropriate notifications will also be made to site PIs, IRBs and health authorities.

Information in this section complies with ICH Guideline E2A: Clinical Safety Data Management: Definitions and Standards for Expedited Reporting, ICH Guideline E-6: Guideline for Good Clinical Practice, 21CFR Parts 312 and 320, and applies the standards set forth in the National Cancer Institute (NCI), CTCAE, Version 4.0: http://ctep.cancer.gov/reporting/ctc.html.

#### 14.2 Definitions

#### 14.2.1 Adverse Event

Any untoward or unfavorable medical occurrence associated with the subject's participation in the research, whether or not considered related to the subject's participation in the research (modified from the definition of AEs in the 1996 International Conference on Harmonization E-6 Guidelines for Good Clinical Practice) (from OHRP "Guidance on Reviewing and Reporting Unanticipated Problems Involving Risks to Subjects or Others and Adverse Events (1/15/07)" http://www.hhs.gov/ohrp/policy/advevntguid.html#Q2)

# 14.2.1.1 Suspected Adverse Reaction

A suspected adverse reaction is any AE for which there is a reasonable possibility that the investigational agents (Section 5) caused the AE. For the purposes of safety reporting, 'reasonable possibility' means there is evidence to suggest a causal relationship between the drug and the AE. A suspected adverse reaction implies a lesser degree of certainty about causality than adverse reaction, which means any AE caused by a drug (21 CFR 312.32(a)).

#### 14.2.1.2 Unexpected Adverse Event

An AE or suspected adverse reaction is considered "unexpected" if it is not listed in the package insert or is not listed at the specificity, severity or rate of occurrence that has been observed; or is not consistent with the risk information described in the general investigational plan or elsewhere in the IND.

"Unexpected" also refers to AEs or suspected adverse reactions that are mentioned in the package insert as occurring with a class of drugs or as anticipated from the pharmacological properties of the drug, but are not specifically mentioned as occurring with the particular drug under investigation (21 CFR 312.32(a).

#### 14.2.2 Serious Adverse Event

An AE or suspected adverse reaction is considered "serious" if, in the view of either the investigator or Sponsor, it results in any of the following outcomes (21 CFR 312.32(a)):

- 1. Death.
- 2. A life-threatening event: An AE or suspected adverse reaction is considered "life-threatening" if, in the view of either the investigator or DAIT/NIAID, its occurrence places the subject at immediate risk of death. It does not include an AE or suspected adverse reaction that, had it occurred in a more severe form, might have caused death.
- 3. Inpatient hospitalization or prolongation of existing hospitalization (Please see Section 0 for exceptions).
- 4. Persistent or significant incapacity or substantial disruption of the ability to conduct normal life functions.
- 5. Congenital anomaly or birth defect.
- 6. Important medical events that might not result in death, be life threatening, or require hospitalization may be considered serious when, based upon medical judgment, they might jeopardize the subject and might require medical or surgical intervention to prevent one of the outcomes listed above.

Confidential Page 57 of 80

# 14.3 Grading and Attribution of Adverse Events

#### 14.3.1 Grading Criteria

The study site will grade the severity of AEs experienced by the study subjects according to the criteria set forth in the NCI-CTCAE — Version 4.0 for all AEs with the exception of Infection. The NCI-CTCAE manual provides a common language to describe levels of severity, to analyze and interpret data, and to articulate the clinical significance of all AEs. The NCI-CTCAE has been reviewed by the study investigators and has been deemed appropriate for the subject population to be studied in this protocol for all AEs with the exception of infection and hematologic events described below.

AEs will be graded on a scale from 1 to 5 according to the following standards in the NCI-CTCAE manual:

- Grade 1 = mild AE.
- Grade 2 = moderate AE.
- Grade 3 = severe and undesirable AE.
- Grade 4 = life-threatening or disabling AE.
- Grade 5 = death.

For any AE of Infection, the following grading system will be used for study participants:

- Grade 1 = asymptomatic; clinical or diagnostic observation only; intervention with oral antibiotic, antifungal, or antiviral agent only; no invasive intervention required
- Grade 2 = symptomatic; intervention with intravenous antibiotic, antifungal, or antiviral agent; invasive intervention may be required
- Grade 3 = any infection associated with hemodynamic compromise requiring pressors; any infection necessitating ICU level of care; any infection necessitating operative intervention; any infection involving the central nervous system; any infection with a positive fungal blood culture; any proven or probable aspergillus infection; any tissue invasive fungal infection; any pneumocystis jiroveci infection
- Grade 4 = life-threatening infection
- Grade 5 = death resulting from infection

Other than those described below, any events grade 2 or higher (including study defined grading of infections) will be recorded on the appropriate AE CRF for this study.

For hematologic events listed below, grade 3 or higher will be recorded on the appropriate AE case report form (CRF) for this study:

- Neutrophil count decreased
- Anemia (Hemoglobin decreased)
- Platelet count decreased
- Total lymphocyte count decreased
- Lymphocyte subset count decreased (including CD4)

Decreased CD4 lymphocytes and lymphocyte counts within 6 months after last study dose of Thymoglobulin® do not require reporting.

For grading an abnormal value or result of a clinical or laboratory evaluation (including, but not limited to, a radiograph, an ultrasound, an electrocardiogram etc.), a treatment-emergent AE is defined as an increase in grade from baseline or from the last post-baseline value that doesn't meet grading criteria. Changes in grade from screening to baseline will also be recorded as AEs, but are not treatment-emergent. If a specific event or result from a given clinical or laboratory evaluation is not included in the NCI-CTCAE manual, then an abnormal result would be considered an AE if changes in therapy or monitoring are implemented as a result of the event/result.

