#### 1.4 Clinical Experience with Treg Therapy

The cellular product to be utilized in this clinical trial has not been previously used in humans. Other relevant clinical experience with Treg infusion is in quite distinct settings. Three trials of Treg therapy for graft versus host disease (GvHD) in patients have been reported (Trzonkowski, 2009) (Brunstein, 2010) (Di lanni, 2011). The first-in-man cases by Trzonkowski et al involved two patients. The first patient had chronic GvHD two years after transplantation. After receiving 0.1 × 10^6/kg fluorescence-activated cell sorting (FACS) purified ex vivo expanded Tregs from the donor, the symptoms subsided and the patient was successfully withdrawn from IS. The second patient had acute disease that progressed despite three infusions with an accumulative dose of  $3 \times 10^6$ /kg expanded donor Tregs. A larger scale phase I trial by Brunstein et al. was reported in 2010 (Brunstein, 2010). Twenty-three patients with advanced hematologic malignancy were enrolled and treated with two units of umbilical cord blood as source of stem cells and effector T cells. Tregs were isolated using anti-CD25 immunomagnetic bead selection from third-party cord blood samples that had 4 to 6 HLA antigen match with the recipient. Up to  $6 \times 10^6$ /kg Tregs, expanded ex vivo using anti-CD3 and anti-CD28 conjugated beads, were infused. The infused Tregs were detectable in circulation for up to 7 days. During the one-year period after Treg infusion, the investigators observed no DLTs or increase in adverse events (AEs) when compared to historical controls. Incidences of severe acute GvHD were significantly reduced in patients who received Treg therapy. The median time to development of GvHD in patients who received Treg infusion was longer compared to normal disease course although the delay was not significant. The third trial enrolled 28 patients with high-risk hematological malignancies (Di lanni, 2011). Patients received anti-CD25 immunomagnetic bead-enriched donor Tregs without ex vivo expansion four days before receiving one haplo-mismatched hematopoietic stem cell and Tconv transplants from the same donors. The majority of Confidential Page 26 of 80

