#### 5.1.2 Dosage, Preparation, and Administration

Confidential Page 36 of 80

The deuterium-labelled darTreg product will be transported within UCSF and between UCSF and remote clinical centers in a shipping container with a temperature monitor and a coolant pack(s) to maintain the temperature between 2°C and 10°C. The product should be maintained in the shipping container until its administration. The infusion of the product must occur within 30 hours after final formulation. The identity of the donor, recipient and the product will be verified by two individuals prior to infusion.

Subjects meeting eligibility criteria for darTreg infusion will receive a single IV dose containing 50 (range 25-60), 200 (range 100-240), or 800 (range 400-960) million darTregs administered in approximately 20-30 minutes by gravity. The line will be primed with saline prior to infusion and the product bag, tubing, and peripheral IV line will be flushed with up to 250ml normal saline to ensure the complete dose is infused.

Pre-medications will be administered prior to infusion (see Section 6.2.2).

Vitals signs will be monitored before, during, and after the infusion. Emergency medical equipment will be available during the infusion in case the subject has an allergic response or an infusion reaction that can result in a CRS. The IV line will be maintained after the infusion and the subject will be asked to remain in the clinical research unit for a minimum of 24 hours which will allow ongoing monitoring for any infusion-related signs and symptoms.

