#### 9.3.2 Risks of autologous ex vivo expanded darTregs infusion

There is limited experience in humans using the darTreg product. Because infusion of *ex vivo* explanded effector T cells has been reported to be associated with infusion reactions, recipients of arTregs should be closely monitored after infusion

Confidential Page 47 of 80

for possible infusion reactions including nausea, hypotension, fevers, chills, and pain. Since the arTreg product is immunosuppressive, possible side effects include over-immunosuppression with increased risks of infections and difficulty clearing infections.

A safety concern of Treg infusion is potential impairment of immune responses to pathogens and/or malignancies. darTregs utilized in this trial are unlikely to possess the full breadth of specificities offered by non-specific, polyclonal Treg pool. Moreover, animal studies suggest that adoptive transfer of alloantigen-specific Tregs does not alter immune responses to viral pathogens (Bushell, 2005). The infusion of Tregs could theoretically impair anti-tumor immunity, which could be of particular concern in transplant recipients at increased risk of PTLD and/or recurrent HCC. With the infusion of darTregs, there is a theoretical possibility that donor reactive T effector cells may be infused and contribute to rejection.

Lastly, an ancillary reagent used in the manufacturing of darTreg is a CD40L-expressing cell line, KT64.CD40L.HLADR0401, which is derived from the human myelogenous leukemia cell line K562. These cells have been irradiated 10,000 rads (5 times the lethal dose); they are therefore not expected to persist in darTreg cultures. To further prevent the infusion of replication competent K562 cells along with the darTregs, the final darTreg product must meet a release criterion of a negative assay for the BCR-ABL translocation, a genetic marker identifying K562 cells. The risk of transmission of myelogenous leukemia in the Treg product is considered to be negligible.

Possible adverse reactions include, but are not limited to, abdominal cramps, anaphylaxis, back pain, chest tightness/pain, and/or chills at the time of infusion, fever ≤38.5°C, flashing, heat/pain at the IV site, hemoglobinuria, hives, mild rigors, nausea, headache, oliguria, pruritus, sever rigors, syncope, tachycardia, vomiting, and wheezing.

Confidential Page 48 of 80

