# 14.4.4 Recording Adverse Events

Throughout the study, the investigator will record AEs and SAEs as described previously (*Section 14.2, Definitions*) on the appropriate AE/SAE form regardless of the relationship to study therapy regimen or study procedure.

Confidential Page 59 of 80

Once recorded, an AE / SAE will be followed until it resolves with or without sequelae, until the end of study participation, or until 30 days after the subject prematurely withdraws (without withdrawing consent) /or is withdrawn from the study, whichever occurs first.

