PBMC Collection Visit does not apply to Cohort 1. Cohort 2 can have whole blood collection for PBMC isolation if hemoglobin is ≥10.5 mg/dl; leukapheresis if <10.5 mg/dl.

<sup>2 Screening for eligibility C1 and C2 can be assessed between 5-6 weeks (30-44 days) after transplantation. Everolimus can be started on or after 30 days after liver transplantation if eligibility criteria are met (Screen C1).

 $^3\mbox{HIV/HBV/HCV}$  serology can be within one year of screening.

<sup>4AFP is only required for subjects known to have HCC. At Screen A, AFP should be drawn if unavailable within 3 preceding months; AFP should be redrawn at time of transplant. After transplant, AFP should be recorded every 3 months.

<sup>5 First EVR level should be obtained within one week of first dose (+/- 2 days). MMF discontinuation and TAC trough 3-5 μg/L for subjects converting to EVR only. Subjects continuing on TAC-based IS should have troughs 6-8 μg/L.

<sup>6 Prior to Thymoglobulin, collect AE's/SAE's occurring within 72 hours after PBMC Collection only. Collect all AE's/SAE's grade 2 and higher from the time of first Thymoglobulin infusion.

<sup>7 Central laboratory assessments may be drawn up to one year BEFORE solumedrol dose in OR. Once drawn, mechanistic labs do not need to be repeated.

<sup>8CBC, Basic Chemistry, Liver Function Tests, and PT/INR/PTT should be collected as close to, but prior to transplant as possible.

<sup>9Liver allograft biopsy should be obtained prior to transplantation (back table) for local pathology reading only, no specimen for central pathology

<sup>10 Screening should take place within 24 hours prior to Thymoglobulin®. The first dose of Thymoglobulin® is to be given within 72 hours after transplantation. Additional doses of 0.75-1.5 mg/kg IV will be administered until CD3 count is ≤50 cells/μL (50 cells/mcL) or total lymphocyte count is ≤ 0.10 x 10 ½L; or when maximum dose of 4.5/mg/kg has been given. Day 2 and Day 6 visits are only needed if Thymoglobulin is given on these days.

 Treg expansion should be initiated 2-3 weeks prior to planned Treg infusion if subjects continue to meet eligibility criteria. Please refer to Stage 3 Schedule of Events. .

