9.5 Vital Signs, Physical Findings, and Other Observations Related to Safety

9.5.1 Vital Signs

Descriptive statistics of vital signs results and change from baseline of vital signs will be summarized for each study group and overall. Data listings will be provided for vital signs measurements. They will be sorted by treatment group, subject, vital sign parameter and time of assessment.

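### Grade 1 darTreg infusion reactions are not required on the AE CRF, so the mild end of tolerability by dose is lost

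*Protocol*

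**What the plan says.** Protocol Section 14.3.1 calls Grade 1 a mild event. It then sets the recording floor: other than the exceptions it lists, "any events grade 2 or higher (including study defined grading of infections) will be recorded on the appropriate AE CRF". Listed blood-count events have a separate, higher floor: "For hematologic events listed below, grade 3 or higher will be recorded on the appropriate AE case report form (CRF) for this study". Appendix 1 footnote 6 repeats the general rule: "Collect all AE's/SAE's grade 2 and higher from the time of first Thymoglobulin infusion". Since darTregs are infused at weeks 11-20, after Thymoglobulin, the Grade 2 floor covers the infusion. Neither place makes an exception for the infusion or the 24-hour stay that Section 5.1.2 requires.

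Section 14.4.4 reads differently: "the investigator will record AEs and SAEs as described previously", pointing back to the definitions in Section 14.2, which contain no grade floor.

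Section 9.3.2 lists possible infusion reactions, among them "hives, mild rigors, nausea, headache, oliguria, pruritus". Section 1.4 says of the product: "The cellular product to be utilized in this clinical trial has not been previously used in humans". Section 2.1 names tolerability as an objective beside safety and dose-limiting toxicities. Safety outcome 5 (Protocol 3.2, SAP 2.1 and 8.1.1) counts infusion reaction and cytokine release at CTCAE Grade 3 or higher.

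Outside the AE form, Section 5.1.2 says: "Vitals signs will be monitored before, during, and after the infusion". SAP 9.5.1 plans: "Descriptive statistics of vital signs results and change from baseline of vital signs will be summarized for each study group and overall". It does not say which measurement is the baseline.

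**The concern.** A Grade 2 floor is reasonable for the crowded course after a liver transplant. It is less reasonable for one supervised day around the infusion of a new cell product. Section 5.4.3 says that the infusion falls in a clinically quiet period well suited to spotting events caused by the cells, so background noise is a weak reason for the floor at that point.

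A rigor judged mild is Grade 1 by Section 14.3.1 and falls below the floor, although Section 9.3.2 expects that such rigors may occur. At stake is the low-grade part of the tolerability description by dose. An event not recorded on the day is hard to recover later.

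The conflict with Section 14.4.4 adds a second problem. One site could record mild reactions and another not. With as few as 3 subjects at a dose, a difference in recording practice could create or hide an apparent dose pattern.

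**Working it through.** **The plan's own figure.** The only precision calculation is Protocol Table 8 (SAP Table 1). Its first row gives 2 events in 216 person-weeks as 0.0093 (0.0011 to 0.0334). Exact Poisson limits reproduce it: lower = χ²(0.025; 4 df)/2/216 = 0.0011; upper = χ²(0.975; 6 df)/2/216 = 0.0334. All 30 rows agree to within rounding. The table concerns rates per person-week by analysis period, with the doses pooled. It does not address low-grade reactions or single dose cohorts, so the size of this point needs its own illustration.

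**Inputs.**
- Subjects per dose: 3 in Cohorts 2 and 3, expandable to 6; 6 in Cohort 4 (Protocol 5.4.1).
- Grade split in the group's earlier polyclonal Treg trial (Protocol 1.4): 58 Grade 1, 25 Grade 2, 8 Grade 3. Check: 58 + 25 + 8 = 91. Grade 1 share 58/91 = 63.7%; Grade 2 or higher 33/91 = 36.3%.
- Assumed, because the documents give no figure: per-subject risk q of an infusion reaction of any grade, 30% to 60%.
- Assumed: the 36.3% share applies to darTreg infusion reactions.

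**Formula.** Chance of recording at least one reaction in n subjects: all grades, 1 − (1 − q)ⁿ; as written, 1 − (1 − q × 33/91)ⁿ.

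| q | n | As written (Grade 2 or higher) | All grades |
|---|---|---|---|
| 30% | 3 | 1 − (1 − 0.109)³ = 29% | 1 − 0.7³ = 66% |
| 60% | 3 | 1 − (1 − 0.218)³ = 52% | 1 − 0.4³ = 94% |
| 30% | 6 | 1 − (1 − 0.109)⁶ = 50% | 1 − 0.7⁶ = 88% |
| 60% | 6 | 1 − (1 − 0.218)⁶ = 77% | 1 − 0.4⁶ = more than 99% |

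**Sensitivity to the borrowed share.** Treating the 91 events as independent, the 95% interval for the Grade 1 share is 53.0% to 73.6%, so the Grade 2 or higher share is 26.4% to 47.0%. For n = 3 the as-written chance becomes:
- q = 30%: 1 − (1 − 0.3 × 0.264)³ = 22% to 1 − (1 − 0.3 × 0.470)³ = 37%.
- q = 60%: 1 − (1 − 0.6 × 0.264)³ = 40% to 1 − (1 − 0.6 × 0.470)³ = 63%.

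This range does not cover the doubt about carrying the share over from another product. At the extremes, if every reaction were Grade 2 or higher nothing would be lost; if every reaction were Grade 1, none would be required on the form.

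**What the fix cannot change.** Zero reactions in 3 subjects has an exact upper 95% limit of 1 − 0.025^(1/3) = 70.8%; zero in 6 has 1 − 0.025^(1/6) = 45.9%. Cohort size limits precision whatever the floor.

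**The case against.** The strongest reply is that the trial already watches the infusion closely and that the missing records would decide nothing. Much of this stands.

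- *Other capture.* Vital signs are taken around the infusion, and Appendix 3 schedules an examination, blood counts, chemistry and liver tests on the infusion day and at 24 hours. SAEs are reported under Section 14.5.1 with no grade floor. Fever or tachycardia may therefore show outside the AE form. But Appendix 3 shows no vital-signs row, SAP 9.5.1 names no infusion time points, and nausea, headache and pruritus are not vital signs. Symptom-only reactions remain the clear gap.
- *No decision depends on it.* Cohort progression rests on the selected events in Section 14.8, and Grade 1 records feed no rule there. This stands: the gain is descriptive.
- *Grades in Section 9.3.2.* Only rigors are labelled mild there. Nausea, hives, headache and pruritus carry no grade, and serious reactions appear in the same list. So the list shows that mild reactions are foreseen, not that most will be mild.
- *Premedication.* All recipients get acetaminophen and diphenhydramine (Section 6.2.2). This may blunt reactions and complicates reading mild events as an effect of dose.
- *Novelty.* Section 1.4 says no previous human use, Section 9.3.2 speaks of limited experience, and Section 4.4 mentions another trial with the same product. On any of these readings there is little prior tolerability data to rely on.

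A reader might infer that Grade 1 events are never recorded. Section 14.4.4 does not support so absolute a reading; the texts conflict. A reader might also infer that tolerability by dose cannot be read at all from 3 subjects per cohort. Cohort 4 has 6 subjects, Cohorts 2 and 3 may expand to 6, and SAP 9.2 tabulates recorded events by cohort and by maximum severity.

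**Conclusion.** The point holds in limited form. The Grade 2 floor on the AE form applies to the darTreg infusion and the stay after it, conflicts with Section 14.4.4, and allows low-grade infusion reactions to go unrecorded. The mild end of the tolerability profile, across cohorts of 3 to 6, is what is lost.

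With an assumed any-grade risk of 30-60% and the borrowed 36% share, the chance of recording at least one reaction in 3 subjects is about 29-52% as written against 66-94% with all grades. Both inputs are assumptions. The share comes from a different Treg product and from AEs of every kind, and the calculation treats subjects as independent.

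Two stronger readings should be resisted. One sets the chance of seeing a Grade 3 reaction against that of seeing any reaction; this overstates the loss, because Grade 2 events are recorded. The other treats mild reactions as the only dose signal available before the next step. Grade 2 events, the one-week biopsy, liver tests and viral DNA are also available. This is a worthwhile, inexpensive improvement, not a flaw in the escalation design.

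**What to change.** In Protocol Section 14.3.1 and Appendix 1 footnote 6, require AEs of any grade to be recorded from the start of the darTreg infusion to the end of the 24-hour stay. State whether the separate floor for listed haematologic events still applies in that window; this point does not require changing it. Keep the Grade 2 floor for the rest of follow-up, and reword Section 14.4.4 so that it refers to the same rule.

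In SAP 8.1.1, add a table of infusion reactions of any grade by dose cohort, with maximum grade per subject. As a minor addition, name the pre-infusion value as the vital-sign baseline in SAP 9.5.1.

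The cost is one CRF instruction, one table and a little extra data entry over one day for 12 to 18 monitored inpatients (3-6 + 3-6 + 6). Mild events will have to be read in the light of the premedication. The change is descriptive and leaves treatment, escalation and stopping rules as they are.
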